2.2 Secondary

2.21 Test the hypothesis that Zevalin RIT will improve progression-free survival.

2.22 Test the hypothesis that Zevalin RIT will improve time to next (any) therapy and time to next chemotherapy.

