16.25 Accrual Rate and Study Duration: The anticipated accrual rate is 4 patients per month. This study is expected to accrue in ~2.75 years. The total study duration is expected to be approximately ~3.25 years, or until the last patient accrued has been observed for at least 6 months.

16.3 Secondary Outcome Analyses: The secondary endpoints listed below will be evaluated in each arm independently and will also be compared between the two arms. Analysis of all endpoints will occur at the time of the primary analysis (after all patients have completed the 6-month disease assessment), after all patients have been followed for 3 years, and after all patients have been followed for 5 years. For all secondary endpoints, p-values <0.001 will be considered statistically significant at either of the first two analyses. At the 5-year analysis, p-values <0.05 will be considered as statistically significant. P-value boundaries are based on the Haybittle-Peto rule.(31, 32) A final analysis for the purpose of providing updated descriptive estimates may be undertaken after all patients have been followed for 10 years.

16.31 Progression-free survival (PFS) is defined as the time from registration to the earliest date documentation of disease progression or death due to any cause. The distribution of progression-free survival time will be estimated using the method of Kaplan-Meier within each arm and compared between the arms using a log-rank test. The progression-free survival rates at 3 years and 5 years will be estimated in each arm.

16.32 Time to any therapy (TTNT) is defined as the time from registration to the date of initiation of any treatment for follicular lymphoma. The distribution of time to any therapy will be estimated using the method of Kaplan-Meier within each arm and compared between the arms using a log-rank test. The percentage of patients free of any therapy at 3 years and 5 years will be estimated in each arm.

16.33 Time to chemotherapy (TTC) is defined as the time from registration to the date of initiation of chemotherapy for follicular lymphoma. The distribution of time to chemotherapy will be estimated using the method of Kaplan-Meier within each arm and compared between the arms using a log-rank test. The percentage of patients free of chemotherapy at 3 years and 5 years will be estimated in each arm.

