16.34 Adverse Events: All eligible patients that have initiated treatment will be considered evaluable for assessing adverse event rate(s). The maximum grade for each type of adverse event will be recorded for each patient, and frequency tables

will be reviewed to determine patterns. Additionally, the relationship of the adverse event(s) to the study treatment will be taken into consideration. Rates of individual adverse events (grade 3 and higher) will be compared between arms using a Fisher's exact test.

16.4 Correlative Research: The correlative endpoints listed below will be evaluated in each arm independently and may also be compared between the two arms. For each measure, values may be investigated with respect to response (CR vs. less than CR) using two-sample t-tests (continuous measures) or chi-square tests (categorical measures). Relationship with time to event measures (PFS, TTNT, TTC) will be evaluated using Kaplan-Meier methods and log-rank statistics (categorical measures) or Cox proportional hazards models (continuous measures). For values collected at more than one time point, changes over time will be evaluated using paired-t-tests (continuous measures) or McNemar's or Bhapkar's tests (categorical measures). Endpoints and additional analyses are described below. Analysis involving quality of life are described in Section 16.47.

- 16.41 The incidence of exon 2 bcl2 mutations will evaluated at baseline.
- 16.42 Tissue Tregs and tissue monocytes will be quantified for the on study tumor biopsies. These values will be reported as percentages.
- 16.43 Serum cytokines will be analyzed for each time point (pre-treatment and 6 months). Each cytokine will be evaluated in reference to normal controls and levels will be categorized as normal, elevated, or suppressed.
- 16.44 Vitamin D levels will be evaluated at on study. At each time point, Vitamin D level will be categorized as normal (sufficient) vs. abnormal (insufficient). Vitamin D insufficiency will be defined as a 25 hydroxy-vitamin D (D2 + D3) level <25 ng/mL in the central (Mayo) laboratory.

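### PFS, time to any therapy and time to chemotherapy are each declared significant at 0.05 at the 5-year analysis with no control across the three, so the chance of at least one false significant result is about 8–14%, depending on correlation, against 5% per test

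*Combined protocol and SAP*

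**What the plan says.** Section 2.2 lists the secondary efficacy aims as hypotheses to be tested. Item 2.21 reads "Test the hypothesis that Zevalin RIT will improve progression-free survival" and item 2.22 reads "Test the hypothesis that Zevalin RIT will improve time to next (any) therapy and time to next chemotherapy". Sections 16.31 to 16.33 give each of the three endpoints its own between-arm log-rank test.

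One significance rule covers them all. Analyses are planned at the time of the primary analysis, after 3 years and after 5 years of follow-up of all patients. The rule is "For all secondary endpoints, p-values <0.001 will be considered statistically significant at either of the first two analyses", followed by "At the 5-year analysis, p-values <0.05 will be considered as statistically significant". Its source is given as "P-value boundaries are based on the Haybittle-Peto rule".

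Section 16 states no order of testing among the three endpoints, no division of alpha, no condition that the primary test must succeed first, and no family-wise level. Section 16.34, under the same heading, adds Fisher's exact tests for individual adverse events of grade 3 and higher.

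**The concern.** Haybittle-Peto limits deal with looking at one endpoint several times. They do nothing about looking at several endpoints. As 16.3 stands, any one of PFS, TTNT or TTC with p<0.05 at 5 years counts as statistically significant, whatever happens to the other two or to the complete response comparison. The plan therefore controls the smaller source of inflation (the looks) and leaves the larger one (three endpoints) open.

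These endpoints matter for how the trial will be read. Section 1.2 puts preventing chemotherapy first among the key issues for these patients, section 1.3 hypothesises more patients progression-free at 3 and 5 years, and section 16.6.2 foresees reporting the three time-to-event endpoints at several follow-up times. An isolated chance result on one of them could be presented as a long-term benefit with more confidence than the 0.05 threshold suggests.

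**Working it through.** **Inputs from the documents.** Three efficacy endpoints (2.2, 16.31–16.33); thresholds 0.001, 0.001 and 0.05 per endpoint (16.3).

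**Assumptions, because the documents are silent.** The log-rank tests are two-sided. The correlation between the three test statistics is varied from 0 to 0.9. The information fractions at the three analyses are 0.2/0.6/1, 0.2/0.65/1 or 0.35/0.75/1.

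**Step 1: the level per endpoint.** The plan states no family-wise figure, so the only level to reproduce is the one for a single endpoint. The sum bound is 0.001 + 0.001 + 0.05 = 0.052. Simulation of one million null trials per setting gives about 0.050–0.051. The repeated looks are under control.

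**Step 2: three endpoints, independent statistics, 5-year analysis only.** 1 − (1 − 0.05)³ = 1 − 0.857375 = 0.1426, or 14.3%. The upper bound under any dependence is 3 × 0.05 = 15%. For false claims in Zevalin's favour alone, at 0.025 each: 1 − 0.975³ = 0.0731, or 7.3%.

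**Step 3: a common positive correlation ρ.** With c = 1.96, the chance of at least one false result is

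1 − ∫ [Φ((c − √ρ·x)/√(1−ρ)) − Φ((−c − √ρ·x)/√(1−ρ))]³ φ(x) dx.

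The version for Zevalin's favour alone keeps only the first Φ term. The column with all three looks comes from simulation.

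| ρ | Two-sided, 5-year only | Two-sided, all three looks | Zevalin's favour only, 5-year |
|---|---|---|---|
| 0 | 14.3% | 14.4–14.5% | 7.3% |
| 0.3 | 13.6% | 13.8% | 6.8% |
| 0.5 | 12.5% | 12.7–12.8% | 6.3% |
| 0.7 | 10.9% | 11.0–11.2% | 5.5% |
| 0.8 | 9.8% | 9.8–10.0% | 4.9% |
| 0.9 | 8.4% | 8.4–8.6% | 4.2% |

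The looks add at most about 0.2 percentage points.

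**Step 4: which part of the range is plausible.** The endpoints overlap by definition. Section 16.32 says "Time to any therapy (TTNT) is defined as the time from registration to the date of initiation of any treatment for follicular lymphoma" and section 16.33 says "Time to chemotherapy (TTC) is defined as the time from registration to the date of initiation of chemotherapy for follicular lymphoma", so every chemotherapy event is also a TTNT event, at or after the first therapy. Treatment also often follows progression. Null trials with linked progression, therapy and chemotherapy times were simulated under these assumptions:

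- 58 patients per arm, median time to progression 5 years, follow-up 5 to 7.75 years;
- 60–90% of patients treated after progression, with a mean delay of 0.3–1.5 years;
- chemotherapy as first therapy in 20–80%.

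Pairwise correlations came out at about 0.4–0.9. The chance of at least one p<0.05 at the final analysis was 8.6%, 10.5%, 12.1% and 12.0% in the four scenarios, or roughly 9–12%.

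**Step 5: after the fix.** With a fixed order, a false claim requires the first true-null endpoint in the order to cross its own limits, which has a probability of about 0.051. With one claim-bearing endpoint the rate is the same.

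**The case against.** Four objections have force.

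**No family-wise promise.** The plan sets a threshold per endpoint, and each endpoint meets it. These endpoints are labelled secondary, and the only decision rule, in 16.21, rests on complete response. Success there leads only to a recommendation for further testing. This stands, and it limits the consequence. It does not remove the problem, because 2.2 frames the three as hypotheses and 16.3 attaches the word significant to each one.

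**No single figure.** A reader might infer that the plan carries a 13% secondary error rate instead of an intended 5%. The documents do not support that. A value near 13% needs a correlation of about 0.4–0.5, which is not stated anywhere, and no 5% family level is stated either. Only a range, set against 5% per test, is defensible.

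**Direction.** The aims in 2.2 are directional, so the harm of interest is a false claim for Zevalin. Under two-sided tests the absolute risk is about half the two-sided figure. The relative inflation is about the same: 6.3% against 2.5% at a correlation of 0.5.

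**Scope.** The rule in 16.3 is worded for all secondary endpoints, and 16.34 adds "Rates of individual adverse events (grade 3 and higher) will be compared between arms using a Fisher's exact test". A reader might infer that the figures or the fix cover these safety comparisons too. They do not; this point concerns the three efficacy endpoints only.

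A reader might also infer that the primary test or the repeated looks are compromised. Neither is: complete response has its own two-sided 0.05, and the looks are controlled to about 0.051 per endpoint.

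**Conclusion.** The gap is real and moderate in size. With no order, split or gate across PFS, TTNT and TTC, the two-sided chance of at least one false significant result, if all three nulls are true, is about 8–14% against 5% per test. In the simulated scenarios with overlapping endpoints it is roughly 9–12%. For false claims in Zevalin's favour alone it is about 4–7% against 2.5%.

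The figures rest on two-sided log-rank tests, correlations between 0 and 0.9, and assumed information fractions and event rates. The absence of control across endpoints does not depend on these assumptions; only its size does. If the log-rank tests were meant to be one-sided at 0.05, the 14.3% at independence would apply to claims in Zevalin's favour, so the sidedness should be stated as well.

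**What to change.** In 16.3, add a fixed testing order for the three efficacy endpoints and keep the Haybittle-Peto thresholds for each. The next endpoint may be declared significant only if the one before it has been. The printed order (PFS, TTNT, TTC) is one option. Because section 1.2 stresses avoiding chemotherapy, the sponsor may prefer another, and should set it before any comparative data are seen.

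Alternatively, name one of the three as the only secondary efficacy endpoint carrying a significance claim, and report the other two with estimates and 95% confidence intervals. Either option holds the three-endpoint family at about 0.051. Say in the same place that the log-rank tests are two-sided, if that is intended, and that the adverse-event comparisons in 16.34 lie outside this family.

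The cost is one or two sentences, with no new patients or data. The downside is that a later endpoint cannot be claimed as significant if an earlier one fails or, under the alternative, that two of the three carry no claim.

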13.0 Treatment/Follow-up Decision at Evaluation of Patient

13.1 Patients will be evaluated per the test schedule during cycle 1 of treatment.

13.2 After treatment, patients will be observed at 3, 6, 9, 12, 18, 24, 30, 36, 48, and 60 months from day 1 of treatment.

13.3 Criteria for removing patients from treatment and initiating observation.

13.3.1 Requested withdrawal or patient non-compliance.

13.4 Patients who have progressive or relapsed disease, receive subsequent treatment for lymphoma, refuse further observation, or fail to return for evaluation during observation will go to event monitoring.

13.5 At 5 years from day 1 of treatment, all patients still on observation will go to event monitoring every 12 months until 10 years from time of registration per Section 18.0.

13.6 A patient is deemed *ineligible* if after registration, it is determined that at the time of registration, the patient did not satisfy each and every eligibility criteria for study entry.

The patient may continue protocol treatment at the discretion of the physician as long as there are no safety concerns, and the patient was properly registered. The patient will continue treatment (if no safety concerns), observation, and event monitoring as specified for all patients (or will be taken off study, if applicable).

- If the patient received treatment, the patient will continue treatment (if no safety concerns), observation, and event monitoring as specified for all patients.
- If the patient never received treatment, On-study material and the End of Active Treatment/Cancel Notification Form must be submitted. No further data submission is necessary.

13.7 A patient is deemed a *major violation*, if protocol requirements regarding treatment in cycle 1 of the initial therapy are severely violated that evaluability for primary end point is questionable. The patient may continue protocol treatment at the discretion of the physician as long as there are no safety concerns, and the patient was properly registered. The patient will continue treatment (if no safety concerns), observation, and event monitoring as specified for all patients.

13.8 A patient is deemed a *cancel* if he/she is removed from the study for any reason before any study treatment is given. On-study material and the End of Active Treatment/Cancel Notification Form must be submitted. No further data submission is necessary.

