16.0 Statistical Considerations and Methodology

16.1 Overview: This is a randomized phase III study designed to compare the complete response rate at 6 months between Rituximab (Arm A) and Zevalin (Arm B) for treatment of asymptomatic follicular lymphoma.

16.11 Primary Endpoint: The primary endpoint of this study is the complete response rate at the 6-month disease assessment which will be compared between the two arms. A patient is considered to be a complete responder if the objective status at the 6-month disease assessment is a complete response. Any patient not meeting the definition of a complete response will be considered as a non-responder for the primary endpoint. A modified intent-to-treat approach will be employed for the primary analysis such that all randomized subjects meeting the eligibility criteria who do not cancel participation prior to treatment initiation and did not experience a major treatment violation (during the first cycle of treatment) will be included in the primary analysis. Sensitivity analysis will be conducted including all patients who did not cancel participation prior to

treatment initiation. The percentage of patients in each response category (e.g., CR, PR, STAB, Relapse/PD) will also be tabulated by arm.

16.2 Statistical Considerations:

16.21 Statistical Design:

Previous studies of treatment with four doses of single agent Rituximab in this patient population have shown CR rates of 6-33% (9 and 10). In addition, preliminary results of an additional study, the RESORT ECOG trial, show a CR rate of 15% in this same population (11). This study is designed to detect an improvement in complete response rate from 20% with Rituximab (Arm A) to 50% with Zevalin (Arm B). The proportion of patients who have a CR at 6 months will be evaluated and compared between the two treatment regimens using a two-sided $\alpha=0.05$ continuity corrected Cochran–Mantel–Haenszel (CMH) test with stratification factors as defined in Section 5.0.

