The primary goal of this trial is to compare the CR rate at 6 months between Rituximab and Zevalin. We will randomize 116 evaluable patients in a 1:1 ratio to Rituximab or Zevalin. This final analysis will take place after all patients have completed the disease assessment at 6 months. A sample size of 58 evaluable patients per arm (116 total evaluable) provides 90% power to detect an improvement in complete response rate from 20% to 50%, using a two-sided chi-square test at a significance level of 0.05. To ensure that 116 evaluable patients are randomized, we will enroll/randomize **128 total patients**.

The CR rate in each arm will be estimated by the number of evaluable patients who achieve a CR as the objective status on the disease assessment at 6 months divided by the total number of randomized evaluable patients in that arm. The CR rates will be compared between the two arms. If the CR rate is higher in the Zevalin arm, where the p-value is less than 0.05, this will be considered sufficient evidence that the Zevalin arm may be recommended for further testing in subsequent studies.

This study will use a dynamic allocation procedure to allocate an equal number of patients to each of the two treatment regimens.(30) This procedure will balance the marginal distributions of the stratification factors between these two treatment arms. The stratification factors that will be used are listed in Section 5.0.

This study will be based on a modified intent-to-treat approach including all randomized patients meeting the eligibility criteria who do not cancel participation prior to treatment initiation and did not experience a major treatment violation (during the first cycle of treatment) based on the randomized treatment assignment.

The study will be permitted to be published after all patients have undergone the 6-month disease assessment to establish the CR rate between each arm. This essentially fulfills the first goal of the study. See Section 16.3 for further analysis plans.

16.23 Other considerations: Adverse events, quality/duration of response, and patterns of treatment failure observed in this study, as well as scientific discoveries or changes in standard care will be taken into account in any decision to terminate the study.

16.24 Sample Size: This study is expected to accrue a maximum of 128 patients unless undue toxicity is encountered.

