For all statistical analyses, p-values <0.05 will be considered statistically significant. For interpreting the clinical significance of effects will be evaluated using the FACT cut-offs described above as well as using Cohen's cut-offs (37): <0.20 =trivial; $0.20-0.50$ =small; $0.50-0.80$ =moderate; and >0.80 =large.

16.5 Data & Safety Monitoring:

- 16.51 The principal investigator(s) and the study statistician will review the study at least twice a year to identify accrual, adverse event, and any endpoint problems that might be developing. The Mayo Clinic Cancer Center (MCCC) Data Safety Monitoring Board (DSMB) is responsible for reviewing accrual and safety data for this trial at least twice a year, based on reports provided by the MCCC Statistical Office.
- 16.52 Adverse Event Stopping Rules (these rules apply to Arm A and Arm B independently): Both Arms A (rituximab) and B (Zevalin) are commercial agents used at the FDA-approved dose with standard CBC and bone marrow criteria. Since the doses are the same, we do not expect any difference in the toxicity profile as described in the label. We note that the Adverse Event Stopping Rule may be adjusted in the event of either (1) the study re-opening to accrual or (2) at any time during the conduct of the trial and in consideration of newly acquired information regarding the adverse event profile of the treatment(s) under investigation. The study team may choose to suspend accrual because of unexpected adverse event profiles that have not crossed the specified rule below.

In our previous study of single-agent rituximab for untreated FL(10), we observed 14% grade 3,4 AEs. In previous Zevalin studies for untreated FL (14) there was, as expected, 15% grade 3 and 17% grade 4 (total 32% grades 3,4) neutropenia that was reversible. There was no grades 3,4 non-hematologic toxicity. These toxicities, if they occur, do so within 12 weeks for both Arms A and B. Accrual will be temporarily suspended to both arms if at any time we observe events considered at least possibly related to study treatment (i.e., an

adverse event with attribute specified as “possible”, “probable”, or “definite”) that satisfy either of the following:

- if 3 or more patients in the first 12 treated patients experience a grade 4 or higher non-hematologic adverse event at least possibly related to treatment.

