17.2 Diagnostic Slides from Original and /or Recurrent Tissue

Central pathology review will be conducted for confirmation of diagnosis by [REDACTED] and colleagues at Mayo Clinic Rochester.

The appropriate representative tumor tissue samples will be forwarded to the Lymphoma SPORE Biospecimens Core for central diagnostic review and classification to confirm the diagnosis. This is a retrospective review to determine the evaluability of the patient's data for analysis. The results of the review are the purposes of the trial only and will not be returned to the site.

Required materials [REDACTED] ():

- Lymphoma Pathology Reporting Form (Complete Section I only)
- Bone marrow biopsy report
- Tumor tissue pathology report
- Tumor tissue diagnostic H&E stained slide
- Tumor tissue immunochemistry or immunophenotyping by flow cytometry report (if available)

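### Section 16.34 leaves treated patients later found ineligible out of the adverse event tables, and no all-treated version is planned

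*Combined protocol and SAP*

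**What the plan says.** - **AE analysis set (16.34).** "All eligible patients that have initiated treatment will be considered evaluable for assessing adverse event rate(s". Two conditions apply: the patient is eligible and has started treatment. Individual events of grade 3 or higher are then compared between arms by Fisher's exact test.
- **Ineligible patients (13.6).** Ineligibility can be established after registration. For such patients the rule is: "If the patient received treatment, the patient will continue treatment (if no safety concerns), observation, and event monitoring as specified for all patients".
- **Central pathology (4.0 footnote 8, 17.2, 18.1).** Patients may be registered on local pathology, and all cases are reviewed centrally later. Section 17.2 describes the purpose: "This is a retrospective review to determine the evaluability of the" patient's data. The submission timetable in 18.1 lists eligibility among the uses of these materials.
- **Complete response (16.11).** The primary analysis is also restricted to eligible patients, but it has a backup: "Sensitivity analysis will be conducted including all patients who did not cancel participation prior to" the start of treatment.
- **Stopping rule (16.52).** Its first limb reads "if 3 or more patients in the first 12 treated patients experience a grade 4 or higher non-hematologic adverse event", with at least possible relation to treatment. It sets no eligibility condition.
- **Significance thresholds (16.3).** "Analysis of all endpoints will occur at the time of the primary analysis", and again at 3 and 5 years. "For all secondary endpoints, p-values <0.001 will be considered statistically significant at either of the first two analyses"; at 5 years the threshold is 0.05. Section 16.34 is numbered under this heading.

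**The concern.** A toxicity table normally describes everyone exposed to the treatment. Here membership depends on a status that can be decided after the patient has been randomised, treated and observed. The plan avoids this in two neighbouring places, the response sensitivity analysis and the stopping rule, but not in the AE comparison.

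The exclusion need not be neutral. Several eligibility criteria concern the marrow and blood counts (3.18, 3.19b, 3.19h, 3.29h), and the marrow report is part of the central review packet (17.2). A patient who was treated and later found to fail one of these criteria is one whose haematological toxicity a reader would want to see. The primary report will set any gain in complete response against toxicity, so both sides should be open to inspection in all treated patients.

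**Working it through.** **Step 1. What the plan's figures can say.** The plan states no AE figure to reproduce. The nearest figures are in 16.21: 116 evaluable patients (58 per arm), then "To ensure that 116 evaluable patients are randomized, we will enroll/randomize" 128. The 58 per arm reproduces with the continuity-corrected two-proportion formula (20% v 50%, two-sided 0.05, 90% power) and is not in dispute. The allowance is 128 - 116 = 12 patients, or 12/128 = 9.4%. It covers three groups, which 16.34 treats differently:

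| Group | Treated? | Removed by 16.34? |
|---|---|---|
| Cancel (13.8) | No | Outside any treated set anyway |
| Major violation (13.7) | Yes | No |
| Ineligible, treated (13.6) | Yes | Yes |

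Only the third group matters here. The 12 is neither an estimate of its size nor a cap on it.

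**Step 2. Effect on a reported rate.** Assume 64 treated in an arm (128/2, no cancels) and about 33% of eligible patients with the event, close to the 32% grade 3-4 neutropenia that 16.52 cites for Zevalin. With x treated-ineligible patients and k events among the eligible, the table shows k/(64 - x). The all-treated rate lies between k/64 (none of the x had the event) and (k + x)/64 (all had it). The width is x/64, about 1.6 percentage points per excluded patient.

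| x (assumed) | Tabulated | All treated, lowest | All treated, highest |
|---|---|---|---|
| 1 | 21/63 = 33.3% | 21/64 = 32.8% | 22/64 = 34.4% |
| 3 | 20/61 = 32.8% | 20/64 = 31.3% | 23/64 = 35.9% |
| 6 | 19/58 = 32.8% | 19/64 = 29.7% | 25/64 = 39.1% |

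The last row is an extreme. Applied to both arms, it would use the whole allowance of 12 on treated-ineligible patients, and its limits require none or all six to have had the event.

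**Step 3. Effect on a test.** Two-sided Fisher p-values, Arm A v Arm B, with two patients excluded from Arm B:

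- All treated 2/64 v 10/64: p = 0.030. If both excluded patients had the event, 2/64 v 8/62: p = 0.052.
- All treated 2/64 v 9/64: p = 0.054. If neither had the event, 2/64 v 9/62: p = 0.029.

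The verdict can move either way, but both starting tables sit next to the 0.05 boundary. If exclusion is unrelated to the event, the first case has probability (10/64)(9/63) = 2.2% given its starting table, and the second (55/64)(54/63) = 73.7%. Averaged over all tables, with one random exclusion per arm of 64, the 0.05 verdict changes in about 2% of trials at assumed rates of 5% v 20%, and in well under 1% at 5% v 32%.

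**Step 4. The thresholds in 16.3, read literally.** With 2 events in Arm A, 10 to 15 events in Arm B give a Fisher p from 0.001 up to 0.05, at both 58 and 64 per arm. With 0 events in Arm A the band is 6 to 10, and with 5 events it is 14 to 20. If 16.3 governs AEs, an unchanged table in these bands would be not significant at the first two analyses and significant at 5 years.

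**The case against.** **Size.** The strongest objection is that little turns on this. Eligibility is verified before registration is accepted (6.4), so treated-ineligible patients should be few. The trial's conclusion rests on the complete response p-value (16.21), and suspension of accrual rests on event counts and percentages (16.52), so no stated decision uses an AE p-value. This stands. It limits the size of the point but does not explain why the AE comparison alone lacks an all-treated version.

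**Hidden toxicity.** A reader might infer that the exclusion hides Zevalin toxicity or weakens safety oversight. The documents do not support that. Section 13.6 keeps these patients under observation, the stopping rule has no eligibility condition, and nothing shows in which arm or direction the exclusions would fall.

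**Changing verdicts.** A reader might also infer that the plan commits itself to judging one fixed AE table by two thresholds. That goes too far. The secondary goals in 2.2 are progression-free survival and time to next therapy or chemotherapy, and 16.6.2 names only time-to-event endpoints for later reports. The link to AEs is the section numbering. Nor is the data set certainly fixed at month 6. Section 18.1 limits AE forms to Cycles 1 and 2, but 10.6 asks for blood count events to be graded at each evaluation, 10.6132 brings in late, possibly related deaths, and 10.62 leaves late events to the forms packet. What remains is an ambiguity to clear up; it affects a label, not the estimated rates.

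**Conclusion.** The main point holds on the text. As written, 16.34 removes observed toxicity in treated patients later found ineligible, and no other section supplies the missing table. The number affected is not given and is probably small, and the direction is unknown. The shift is at most about 1.6 percentage points per excluded patient in an arm of 64, and test verdicts change only at boundary counts. These sizes rest on assumed arm sizes, event rates and exclusion counts. Efficacy results, AE collection and monitoring are unaffected.

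The question of which threshold applies to AEs is a secondary clarification. Separately, 18.1 footnote 3 limits expedited reports to Cycles 1 and 2, while 10.4 footnote 1 requires related serious events to be reported beyond 30 days with no such end date. These passages contradict each other and must be reconciled.

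**What to change.** 1. **Section 16.34.** Define the AE analysis set as all patients who received any study treatment, regardless of eligibility. This is one sentence and needs no new data, because 13.6 already keeps these patients in follow-up. The AE and response tables will have different denominators, which a footnote can explain.
2. **Sections 16.3 and 16.34.** State whether the Haybittle-Peto thresholds apply to AE comparisons. If they are not meant to, say so, report the month 0-6 comparison at the primary analysis as rate differences with confidence intervals, and summarise any later AEs descriptively. This is one or two sentences, and it avoids a significance label on many AE terms.
3. **Sections 18.1 and 10.4.** Reconcile the two footnotes on late expedited reporting. This may change which late serious events are collected, so it costs more than a wording edit.
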